### 8.1.2.2 Primary Estimand

The primary estimand for PFS is the difference in survival functions between treatment conditions in the duration of radiographic progression-free survival in the targeted population:

- irrespective of whether the assigned study treatment was given
- irrespective of clinical deterioration
- irrespective of whether local radiation was given to bone
- irrespective of surgical resection of non-target lesions
- irrespective of local non-protocol anti-cancer treatment other than for disease under study
- had surgery to resect tumor lesions not occurred
- had systemic non-protocol anti-cancer treatment not been given
- had local non-protocol anti-cancer treatment for disease under study not been given
- had local radiation to soft tissue not been given

Derived as follows:

**Table 6: Primary Estimand Attribute for PFS**

| Estimand attribute                                    | Primary definition  |                  |
|---|---|------------------|
| Population  | Subjects randomized into the study intended to include patients with radioiodine-refractory DTC who have progressed after prior VEGFR-targeted therapy. |                  |
| Endpoint  | Duration of radiographic progression-free survival  |                  |
| Intercurrent events   | Event   | Strategy         |
|   | Receipt of assigned study treatment   | Treatment policy |
|   | Clinical deterioration  | Treatment policy |
|   | Receipt of local radiation to bone  | Treatment policy |
|   | Surgical resection of non-target tumor lesions  | Treatment policy |
|   | Receipt of local non-protocol anti-cancer medications other than for disease under study  | Treatment policy |
|   | Surgical resection of target tumor lesions  | Hypothetical     |
|   | Receipt of systemic non-protocol anti-cancer medications  | Hypothetical     |
|   | Receipt of local non-protocol anti-cancer medications for disease under study   | Hypothetical     |
| Receipt of local radiation to soft tissue for disease under study | Hypothetical  |                  |
| Population summary  | Difference in survival functions between treatment conditions.  |                  |

 See Appendix E for estimand terminology

### 8.1.2.3 Alternative Estimands

Two alternative estimands for PFS are defined as below, arising from changes in strategy for handling some intercurrent events. Shaded cells differ from primary estimand. Alternative estimand 1 changes the strategy for selected clinical intercurrent events to “composite,”

resulting in an endpoint that comprises radiographic and clinical progression (as well as death). Alternative estimand 2 changes the strategy to “composite” only for systemic non-protocol anti-cancer medications, yielding an endpoint that comprises radiographic progression, death, or initiation of systemic NPACT.

**Table 7: Alternative Estimand Attribute for PFS**

| Estimand attribute | Alternative 1 definition   |                  | Alternative 2 definition   |                  |
|---------------------------|---|------------------|---|------------------|
| Population                | Subjects randomized into the study intended to include patients with radioiodine-refractory DTC who have progressed after prior VEGFR-targeted therapy. |                  | Subjects randomized into the study intended to include patients with radioiodine-refractory DTC who have progressed after prior VEGFR-targeted therapy. |                  |
| Endpoint                  | Duration of radiographic and clinical progression-free survival   |                  | Time to radiographic progression, death, or initiation of systemic NPACT  |                  |
| Intercurrent events       | Event  | Strategy  | Event  | Strategy  |
|                           | Receipt of assigned study treatment   | Treatment policy | Receipt of assigned study treatment   | Treatment policy |
|                           | Clinical deterioration  | Composite        | Clinical deterioration  | Treatment policy |
|                           | Receipt of local radiation to bone  | Treatment policy | Receipt of local radiation to bone  | Treatment policy |
|                           | Surgical resection of non-target tumor lesions  | Treatment policy | Surgical resection of non-target tumor lesions  | Treatment policy |
|                           | Receipt of local non-protocol anti-cancer medications other than for disease under study  | Treatment policy | Receipt of local non-protocol anti-cancer medications other than for disease under study  | Treatment policy |
|                           | Surgical resection of target tumor lesions  | Composite        | Surgical resection of target tumor lesions  | Hypothetical     |
|                           | Receipt of systemic non-protocol anti-cancer medications  | Composite        | Receipt of systemic non-protocol anti-cancer medications  | Composite        |
|                           | Receipt of local non-protocol anti-cancer medications for disease under study   | Composite        | Receipt of local non-protocol anti-cancer medications   | Hypothetical     |
|                           | Receipt of local radiation to soft tissue for disease under study   | Composite        | Receipt of local radiation to soft tissue for disease under study   | Hypothetical     |
| Population summary        | Difference in survival functions between treatment conditions.  |                  | Difference in survival functions between treatment conditions.  |                  |

#### 8.1.2.4 Primary Definition

For the primary analysis directed toward the primary estimand, duration of PFS is defined as the time from randomization to the earlier of either the date of radiographic progression per BIRC or the date of death due to any cause.

$$\text{PFS (months)} = (\text{earliest date of progression, death, censoring} - \text{date of randomization} + 1) / 30.4375$$

General censoring rules for the primary analysis of PFS are described below, with details provided in Table 8(analysis ID PFS-EP-1):

- Subjects who receive systemic NPACT, or local NPACT for disease under study, or non-protocol radiation therapy for disease under study (other than to bone) or surgery to resect target lesions before experiencing an event will be right censored at the date of the last ATA on or prior to the date of initiation of subsequent therapy/surgery. If there is no such tumor assessment after randomization, the subject will be right censored on the date of randomization.
- Subjects who have not experienced an event (and are not otherwise censored) at the time of data cutoff will be right censored on the date of their last tumor assessment after randomization that is on or prior to the data cutoff. If there is no such tumor assessment after randomization, the subject will be right censored on the date of randomization.
- Subjects who miss two or more ATAs (operationally defined as an interval of 126 days in the first year and 196 days after the first year without an ATA) followed by an event (progression or death) will be right censored on the date of their most-recent ATA prior to the missing assessments. If there is no such tumor assessment after randomization, the subject will be right censored on the date of randomization.

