### **7.1.2 Prohibited or Restricted Therapies**

*The following therapies are prohibited until study treatment has been permanently discontinued:*

- Any investigational agent or investigational medical device.
- Therapeutic doses of oral anticoagulants (eg, warfarin or other coumarin-related agents, direct thrombin or direct FXa inhibitors, or antiplatelet agents such as clopidogrel, or chronic use of aspirin above low dose levels for cardioprotection per local applicable guidelines).
- Any nonprotocol systemic anticancer treatment (eg, chemotherapy, immunotherapy, radionuclides, drugs or herbal products used specifically for the treatment of DTC).

*The following therapies should be avoided until study treatment has been permanently discontinued or until otherwise specified:*

- Local anticancer treatment including palliative radiation, ablation, embolization, or surgery with impact on tumor lesions should not be performed until radiographic progression per RECIST 1.1 has been established. If clinically unavoidable the investigator should consult the Sponsor prior to the procedure for safety guidance.
- Erythropoietic stimulating agents (eg, epoetin alfa and darbepoetin alfa) should not be used based on a report of increased risk of tumor recurrence/progression associated with erythropoietin (Wright et al 2007).
- Concomitant medications that are known to prolong the QTc interval should be avoided in subjects who receive cabozantinib until they have permanently discontinued cabozantinib treatment (refer to <http://www.qtdrugs.org> for a list of drugs which have the potential to prolong the QTc interval).
- Chronic co-administration of cabozantinib with strong inducers of the CYP3A4 family (eg, phenytoin, carbamazepine, rifampin, rifabutin, rifapentine, phenobarbital, and St. John's Wort) may significantly decrease cabozantinib concentrations and should be avoided. Selection of alternate concomitant medications with no or minimal CYP3A4 enzyme induction potential is recommended. See Appendix E for further details.
- Caution must be used when discontinuing treatment with a strong CYP3A4 inducer in a subject who has been concurrently receiving a stable dose of cabozantinib, as this could significantly increase the exposure to cabozantinib.

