## **6.9 Post-randomization Radiotherapy, Surgery/Procedure**

Post-randomization radiation therapy and surgery/procedures that impacted the target lesion(s) (Yes, No, Unknown) will be summarized by treatment group for subjects in the OITT, ITT, O-Safety and Safety populations.

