**Table 5: Primary Estimand Attribute for ORR**

| Estimand attribute  | Primary definition for study  |                     |
|---------------------------------|---|---------------------|
| Population                      | Subjects randomized into the study intended to include patients with radioiodine-refractory differentiated thyroid cancer who have progressed after prior VEGFR-targeted therapy. |                     |
| Endpoint                        | Radiographic response per RECIST 1.1  |                     |
| Intercurrent events             | Event   | Strategy            |
|                                 | Receipt of assigned study treatment   | Treatment policy    |
|                                 | Receipt of local radiation to bone  | Treatment policy    |
|                                 | Surgical resection of non-target tumor lesions  | Treatment policy    |
|                                 | Death   | Treatment policy    |
|                                 | Loss to radiographic follow up  | Treatment policy    |
|                                 | Receipt of local non-protocol anti-cancer medications other than for disease under study  | Treatment policy    |
|                                 | Surgical resection of target tumor lesions  | While on treatment* |
|                                 | Receipt of systemic non-protocol anti-cancer medications  | While on treatment* |
|                                 | Receipt of local non-protocol anti-cancer medications for disease under study   | While on treatment* |
|                                 | Receipt of local radiation to soft tissue for disease under study   | While on treatment* |
| Population summary              | Difference in proportions of subjects with a best overall response of confirmed complete response or confirmed partial response per RECIST 1.1 between treatment conditions.      |                     |
| Estimator                       | Fisher's exact test   |                     |

 See Appendix E for estimand terminology

\* A modified version of the “while on treatment” strategy is employed for these intercurrent events. Only data prior to the occurrence of these intercurrent events is of interest, but under the ITT principle, receipt of study treatment itself is not considered.

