| Systemic NPACT (medications)   | censored        | date of last ATA* before first initiation of therapy                     | censored                      | date of last ATA* before first initiation of therapy                     | censored               | date of last ATA* before first initiation of therapy                     | censored                                   | date of last ATA* before first initiation of therapy                     |
| Local NPACT for disease under study (medications)                                      | censored        | date of last ATA* before first initiation of therapy                     | censored                      | date of last ATA* before first initiation of therapy                     | censored               | date of last ATA* before first initiation of therapy                     | censored                                   | date of last ATA* before first initiation of therapy                     |
| Surgical resection of target tumor lesion(s)   | censored        | date of last ATA* before target lesion resection                         | censored                      | date of last ATA* before target lesion resection                         | censored               | date of last ATA* before target lesion resection                         | censored                                   | date of last ATA* before target lesion resection                         |
| Local radiation: to soft tissue for disease under study                                | censored        | date of last ATA* local radiation of soft tissue for disease under study | censored                      | date of last ATA* local radiation of soft tissue for disease under study | censored               | date of last ATA* local radiation of soft tissue for disease under study | censored                                   | date of last ATA* local radiation of soft tissue for disease under study |
| Missing data   |                 |  |                               |  |                        |  |  |  |
| No baseline ATA  | censored        | date of rand.  | censored                      | date of rand.  | censored               | date of rand.  | censored                                   | date of rand.  |

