| ≥ 2 consecutive missing scheduled ATA immediately prior to analysis event              | censored        | date of last ATA* before missing visits                                  | censored                      | date of last ATA* before missing visits                                  | censored               | date of last ATA* before missing visits                                  | event                                      | date of last ATA* before missing visits                                  |
| Observation ongoing  |                 |  |                               |  |                        |  |  |  |
| None of the above  | censored        | date of last ATA*  | censored                      | date of last ATA*  | censored               | date of last ATA*  | censored                                   | date of last ATA*  |

ATA, adequate tumor assessment; BIRC, blinded independent review committee; ITT, intent-to-treat; NA, not applicable; PD, progressive disease; NPACT, non-protocol anti-cancer therapy (medications including radiopharmaceuticals but excluding local radiation)

Date of recorded PD = see SAP text.

\* or date of randomization if no post-randomization ATA

Blue cells indicate changes from primary analysis.

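### In SAP Table 8, resection is the only non-drug, non-radiation procedure on a target lesion that censors PFS; text and tables conflict on whether ablation and embolization count as local NPACT

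*Combined protocol and SAP*

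**What the plan says.** Four kinds of therapy end the primary PFS window. SAP 8.1.2.4 begins: "Subjects who receive systemic NPACT, or local NPACT for disease under study, or non-protocol radiation therapy for disease under study (other than to bone"), and then adds "or surgery to resect target lesions before experiencing an event will be right censored at the date of the last ATA". The same section makes Table 8 the detailed rule: "General censoring rules for the primary analysis of PFS are described below, with details provided in Table 8" (analysis PFS-EP-1).

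Table 8 narrows two of these. Its local-therapy row reads "Local NPACT for disease under study (medications"), and its footnote defines "NPACT, non-protocol anti-cancer therapy (medications including radiopharmaceuticals but excluding local radiation"). Apart from radiation, the only procedure with a row is resection of target lesions.

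The ORR estimand follows the same pattern. Table 5 lists "Surgical resection of target tumor lesions", and both that table and SAP 8.1.1.2 confine local NPACT to medications. SAP 8.1.1.1 closes the best-overall-response window at the censoring events of the primary PFS analysis.

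Protocol 7.1.2 foresees other procedures: "Local anticancer treatment including palliative radiation, ablation, embolization, or surgery with impact on tumor lesions should not be performed until radiographic progression" is established. The section goes on to allow for clinically unavoidable cases after consultation with the Sponsor. SAP 6.9 plans to report them: "Post-randomization radiation therapy and surgery/procedures that impacted the target lesion(s) (Yes, No, Unknown) will be summarized by treatment group".

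**The concern.** The estimands set aside tumor change that follows physical removal of a target lesion. Ablating or devascularizing the same lesion can change the sum of diameters in the same way, yet under Table 8 one is censored and the other is not, and no reason is given. Both primary endpoints are exposed, because the response window takes its end points from the PFS rule. A subject could become a responder, or escape progression, because of a procedure and not because of study treatment.

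Since the narrative text can be read more broadly than the table, two programmers could also handle the same subject differently in a primary analysis.

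**Working it through.** No figure in the plan decides this point, so the passages are compared first and the possible size follows.

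**Passages that would take in ablation or embolization**
- SAP 8.1.2.4 names local NPACT for the disease under study, with no limit to medications.
- SAP 8.1.2.2, the PFS estimand text, speaks of local anti-cancer *treatment*.
- Protocol 5.4.2 collects each NPACT by the name of a drug or a procedure.
- Protocol 7.1.2 classes ablation and embolization as local anticancer treatment.

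**Passages that leave them out**
- SAP Table 8, its footnote, and Table 9 use *medications*.
- Table 6 uses *medications* for the estimand whose text says *treatment*.
- SAP 8.1.1.2 and Tables 5 and 7 use *medications*.
- SAP 6.8 summarizes non-radiation NPACT by ATC text and WHO Drug name, which is drug coding. Procedures that impacted target lesions are reported separately in 6.9, with no link to censoring or best overall response.
- Protocol 9.2.2.2 censors for systemic NPACT, non-bone radiation and target-lesion resection; local NPACT does not appear.

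Because 8.1.2.4 defers to Table 8, a programmer following the detailed rule would not censor for thermal ablation or bland embolization.

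**Sensitivity analyses.** PFS-EP-2 to PFS-EP-4 and the Table 9 analyses reuse the same situation rows. PFS-EP-11 to PFS-EP-14 reclassify investigator-only progression, stopped imaging and systemic NPACT. None addresses these procedures.

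**Effect on one subject** (illustrative lesions, thresholds from protocol Appendix H). Target lesions of 40 and 20 mm give a baseline sum of 60 mm.
- False PR: the 20 mm lesion is ablated and read as 0, the other is unchanged. The sum is 40 and the change is (60 − 40)/60 = 33% decrease, beyond the 30% needed for PR. The lesion may still read 0 at a scan at least 28 days later, so confirmation need not remove it.
- Masked PD: both lesions would have grown 20%, to 48 + 24 = 72. That is (72 − 60)/60 = 20% and 12 mm, hence PD. With the smaller lesion ablated and read as 0, the sum is 48, or (60 − 48)/60 = 20% decrease, hence SD. This needs the procedure to fall between the last scan and the one that would have shown PD. Had an earlier post-procedure scan set a nadir of 40, then 48 would be (48 − 40)/40 = 20% and 8 mm, which is PD.

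**Number of subjects.** The documents give no frequency. Assuming 1–3% have such a procedure: 0.01 × 300 = 3 to 0.03 × 300 = 9 for PFS, and 1 to 3 of the 100 in the ORR analysis.

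**Effect on the ORR test** (assumed split 67:33; design rates 35% and 2% from SAP 2.4; two-sided Fisher test at 0.01). Expected responders are 0.35 × 67 = 23.5 and 0.02 × 33 = 0.66.

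| Responders, cabozantinib vs placebo | Fisher p |
|---|---|
| 23/67 vs 1/33 | 0.0003 |
| 20/67 vs 1/33 (three removed) | 0.0014 |
| 16/67 vs 1/33 | 0.0096 |
| 15/67 vs 1/33 | 0.018 |

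Near the design rates, three reclassified subjects do not change the result. One subject matters only if the outcome lands at the boundary.

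**The case against.** A reader who starts at the surgery clause might infer that resection is the only thing that ends the two windows. The documents do not support that: systemic NPACT, local NPACT for the disease under study and non-bone radiation censor as well, in 8.1.2.4 and in Table 8.

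A reader might also infer that the plan overlooks ablation and embolization everywhere. It does not. On 8.1.2.4, 8.1.2.2 and protocol 5.4.2 they can be counted as local NPACT and censored, and SAP 6.8 itself refers to NPACT as including radiation, so the Table 8 footnote is not a uniform definition. Embolization that delivers a drug or radiopharmaceutical could fit even the medications row. These arguments stand, and they make the defect partly a conflict between text and tables. They do not settle it, because the text defers to the table.

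It would also be too strong to say that such shrinkage will count as response or will hide progression. The procedure must precede BIRC progression, which protocol 7.1.2 discourages. For a false PR the treated lesion must make up about 30% or more of the sum, with no offsetting growth elsewhere. The reader must record 0 mm and not call the lesion unable to evaluate, there must be no new lesion or non-target progression, and the response must be confirmed. The imaging and BIRC charters, which are not among the documents, may govern treated lesions. However, Appendix H has no rule for target lesions treated locally after baseline, and the only treatment information the protocol describes as going to the BIRC is prior radiation history. The consequence is therefore possible, not shown.

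**Conclusion.** The point holds in limited form. Under Table 8, thermal ablation or bland embolization of a target lesion leaves the subject in the PFS and response windows, while resection of the same lesion censors. The narrative text and the tables disagree on whether that is intended.

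The effect is probably small. The 1–3% is an assumption about procedures performed, not subjects misclassified. Direction by arm is unknown, and a false placebo responder would count against cabozantinib. No effect on the PFS hazard ratio can be computed from the documents. The verdict rests on Table 8 being the rule programmed and on no charter rule for treated lesions. It is worth settling before unblinding because it touches both primary endpoints and costs little.

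**What to change.** - Keep the resection row. In SAP 8.1.1.2, 8.1.2.2, 8.1.2.4 and Tables 5–9, add after it: *or other non-drug local procedure (e.g., ablation, embolization) recorded as having impacted a target lesion (SAP 6.9 = Yes)*. Give it the strategy each table now gives resection. Adding, not replacing, avoids losing a resection whose 6.9 entry is not *Yes*.
- State how *Unknown* in 6.9 is handled, for example by blinded query before database lock.
- Use one term, *treatment* or *medications*, for local NPACT throughout the text and tables, and make the Table 8 footnote match.

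The cost is SAP wording and use of an item the SAP already plans to summarize. Sample size and event count do not change. The downside is that a few more subjects may be censored.

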2. **Brain:** MRI (or CT) of the brain will be performed in all subjects at screening. After randomization, MRI (or CT) scans of the brain are only required in subjects with known brain metastasis following the same post-baseline frequency as the imaging for CAPN. MRI is the preferred imaging method for brain. If CT of the brain is performed instead of MRI, ambiguous results must be confirmed by MRI. (Note: In order to meet the eligibility requirements of the study, brain metastasis must have been treated and stable for at least 4 weeks before randomization. Subjects without documented brain metastasis during the screening assessment are not required to undergo post-randomization brain imaging unless clinically indicated.)
3. **Bone scans:** Technetium bone scans will be performed at screening in all subjects and after randomization only in subjects with known bone metastasis every 24 weeks ( $\pm$  14 days). Technetium bone scans are also to be performed for clinical symptoms indicative of new bone metastases. Bone scan findings alone cannot be used for the determination of progression or response per RECIST version 1.1 and need to be corroborated by CT or MRI.

Tumor assessments are to continue on the protocol-defined schedule (Appendix A) relative to the date of randomization regardless of whether study treatment is given, reduced, held, or discontinued, including for subjects randomized to placebo who cross over to receive cabozantinib (Appendix B). The same imaging modalities used at screening will be used for subsequent tumor assessments after randomization.

Investigators should, if any doubt or ambiguities exist about radiographic progression, have subjects continue study treatment if the subject is tolerating it acceptably, repeat radiographic tumor imaging at the next scheduled time point, and delay determination of progression until the findings indicating radiographic progression are unequivocal.

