### **9.2.2.2 Progression-Free Survival (PFS)**

The primary analysis of the co-primary endpoint of PFS will be performed among subjects in the ITT population. It is designed to include radiographic progression events as determined by the BIRC per RECIST 1.1 and deaths due to any cause. Clinical deterioration or radiographic progression determined by the investigator will not be considered progression events in the primary analysis of PFS.

General censoring rules for the primary analysis of PFS are described below:

- Subjects who receive systemic NPACT or nonprotocol radiation therapy (other than to bone) or surgery to resect target lesions before experiencing an event will be right censored at the date of the last tumor assessment prior to the date of initiation of subsequent therapy/surgery. If there is no such tumor assessment post randomization, the subject will be right censored on the date of randomization.
- Subjects who have not experienced an event (and are not otherwise censored) at the time of data cutoff will be right censored on the date of their last tumor assessment post randomization that is on or prior to the data cutoff. If there is no such tumor assessment post randomization, the subject will be right censored on the date of randomization.
- Subjects who miss two or more scheduled tumor assessments followed by an event will be right censored on the date of their most-recent tumor assessment prior to the missing assessments. If there is no such tumor assessment post randomization, the subject will be right censored on the date of randomization.

The analysis of PFS is event-based and will be conducted after at least 193 events (progression per RECIST 1.1 per BIRC or death) have been observed in the ITT population (see Section 9.10).

Hypothesis testing between the two treatment arms will be performed using the stratified log-rank test with a 2-sided, 0.04 or 0.05 level of significance (see Section 9.9). The stratification factors are those used to stratify the randomization (see Section 3.4).

The median duration of PFS and the associated 95% CI for each treatment arm will be estimated using the Kaplan-Meier method. The stratified HR and its 96% or 95% CI will be estimated using a Cox proportional-hazard model with treatment group as the independent variable. The stratification factors will be the same as those used to stratify the randomization.

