##### **8.1.2.1 Definitions and Conventions**

For tumor assessment, CT or MRI of chest/abdomen/pelvis/neck (CAPN) will be performed at screening and every 8 weeks ( $\pm 7$  days) after randomization during the first 12 months on study. Upon subject completion of 12 months on study, these assessments will be performed every 12 weeks ( $\pm 14$  days).

The recorded date of radiographic progression is the date of the tumor assessment visit at which progression is declared. If multiple scan dates are associated with a tumor assessment visit, the earliest assessment date within the set will be chosen as the progression date.

Only adequate tumor assessments (ATAs) will be considered in the determination of radiographic progression and censoring dates. For the purpose of this study, an ATA is defined as one that results in a time point assignment of: response (complete or partial), stable disease/(non-CR, non-PD), or progression. For PFS, ATA is based on soft tissue evaluation by CT/MRI.

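### The 126-day and 196-day limits for two missed scans do not fit a gap that crosses month 12, and the SAP does not say which limit applies there

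*Combined protocol and SAP*

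**What the plan says.** Protocol 9.2.2.2 states the censoring rule as a count: "Subjects who miss two or more scheduled tumor assessments followed by an event will be right censored". SAP Table 8 has the same rule, as two or more consecutive scheduled ATAs missed just before the event, and it gives no day limits. SAP 8.1.2.4 turns the count into days, "operationally defined as an interval of 126 days in the first year and 196 days after the first year without an ATA". A subject who meets the limit "will be right censored on the date of their most-recent ATA prior to the missing assessments", so the event is lost and follow-up is cut back to that scan.

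The schedule is in SAP 8.1.2.1. Scans are every 8 weeks, with a window of 7 days either side, for the first 12 months. "Upon subject completion of 12 months on study, these assessments will be performed every 12 weeks", with a window of 14 days either side. Protocol 5.7.6.1 fixes the anchor: "Tumor assessments are to continue on the protocol-defined schedule (Appendix A) relative to the date of randomization". Neither document gives the week of the first 12-weekly scan. The SAP also does not say whether the last ATA, the missed visit or the event decides which year a gap belongs to, or whether a gap equal to the limit meets it.

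**The concern.** A day limit can stand in for a count of missed scans only if it separates one missed scan from two. That depends on the scan interval, which changes at month 12. A gap that spans the change contains both intervals, so a limit built from either one alone can misclassify it.

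This decides which events count in PFS-EP-1, the primary analysis of a primary endpoint. Two programmers working from the same text could build different primary datasets. The missed-ATA rule also appears in the other columns of Tables 8 and 9, and duration of response takes its dates from the PFS-EP-1 and PFS-EP-3 columns (SAP 8.4.2). A choice made after unblinding would be a choice about which primary events to keep.

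**Working it through.** **Reproducing the limits.** The longest gap with exactly one missed scan is two intervals plus the window at each end.

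- 8-weekly: 2 × 56 + 2 × 7 = 126 days.
- 12-weekly: 2 × 84 + 2 × 14 = 196 days.

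Both match the SAP. Within one schedule they work: the shortest gap to a scheduled scan with two missed is 3 × 56 − 14 = 154 days, or 3 × 84 − 28 = 224 days.

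**Gaps that cross month 12.** Assume scans at Weeks 40, 48, 60 and 72, with a 7-day window up to Week 48 and a 14-day window after. The range is the nominal gap plus or minus 7 + 14 = 21 days.

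| Last ATA | Missed | Progression seen | Nominal gap (days) | Range | 126 days (year set by last ATA) | 196 days (year set by event) |
|---|---|---|---|---|---|---|
| Week 40 | 48 | Week 60 | 20 × 7 = 140 | 119–161 | censored at nominal dates | counted |
| Week 48 | 60 | Week 72 | 24 × 7 = 168 | 147–189 | always censored | counted |
| Week 32 | 40, 48 | Week 60 | 28 × 7 = 196 | 175–217 | censored | counted if under 196; at exactly 196 it depends on the comparison used |
| Week 40 | 48, 60 | Week 72 | 32 × 7 = 224 | 203–245 | censored | censored |

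The count rule would keep the first two rows as events and censor the last two. Dating by the last ATA gets the first two wrong. Dating by the event gets part of the third wrong.

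**Other readings of the schedule.**

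- First 12-weekly scan at Week 56, then Week 68: the one-miss gaps are 112 days (91–133) and 140 days (119–161), so 126 can still be exceeded. Last ATA at Week 32 with two missed gives 168 days (147–189), which the event-date reading always counts.
- First 12-weekly scan at Week 64, then Week 76: the one-miss gaps are 168 days (147–189) and 196 days (175–217), so even the 196-day limit can censor an event after one missed scan.

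**Size.** The inputs from the plan are exponential PFS with medians of 5.5 and 9.0 months, 200 and 100 subjects, 15 months of accrual and a cut-off at month 20. These give about 119 + 76 = 195 events, in line with the planned 193. All events are treated as progression. On the Week 48/60/72 schedule, the expected numbers of subjects whose progression time fits the two one-miss patterns are:

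- cabozantinib: 12.09 + 6.76 = 18.85, or 9.4 per 100 randomised;
- placebo: 5.70 + 2.87 = 8.57, or 8.6 per 100 randomised;
- total: 27.42.

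The documents give no missed-scan rate m, so 5% to 20% is an assumption. A wrongly censored event needs the last ATA done, the next scan missed and the following scan done, so the expected number is 27.42 × m × (1 − m)²:

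- 5%: 27.42 × 0.05 × 0.9025 = 1.2;
- 10%: 27.42 × 0.10 × 0.81 = 2.2;
- 20%: 27.42 × 0.20 × 0.64 = 3.5.

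Simulations that add the visit windows give 1.0 to 1.2, 2.2, and 3.2 to 3.5. With the first 12-weekly scan at Week 56 they give about 0.5, 0.9 and 1.4. Dating by the event misclassifies fewer than 0.5 events on the Week 60 schedule and up to 0.9 on the Week 56 schedule.

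When the gap is dated by the last ATA, the simulated hazard ratio moves from 0.619 to 0.618, from 0.615 to 0.614 and from 0.608 to 0.606 at the three rates.

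**The case against.** The strongest reply is that the SAP already holds the correct rule. SAP 8.1.2.4 calls its bullets general and refers to Table 8 for detail, and Table 8 counts missed scheduled ATAs. On that view the day limits are shorthand, and dating by the event makes them nearly harmless on the Week 60 schedule. This carries weight and keeps the point small. It does not remove it: the day limits are given as the operational definition, nothing says the table prevails, and the event-date reading is only one of those open to a programmer.

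SAP 4.9 also allows operational clarifications by addendum before unblinding, and PFS-EP-4 counts events after a missed-ATA gap instead of censoring them. But PFS-EP-4 dates them at the last ATA before the gap, not at the observed progression, and it relies on the same missed-ATA definition. It covers the issue only in part.

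A reader might infer a bias between arms, because mostly cabozantinib subjects remain at risk after month 12. The candidate events, at 9.4 and 8.6 per 100 randomised, roughly follow the 2:1 allocation and show no meaningful imbalance. A reader might also take SAP 9.9 as support for a high missed-scan rate. It says that pandemic summaries may include patterns of missing data, and it predicts no rate.

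Deaths between visits are a separate matter. Any day limit can miscount them, also within the first year. With the last ATA at day 56, Weeks 16 and 24 missed (the Week 24 window closes at day 175) and death at day 180, the gap is 124 days. The death counts although two scans were missed, so such cases say nothing specific about month 12.

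**Conclusion.** The point stands as a minor defect in the primary PFS rule. For gaps that cross month 12, neither limit reproduces the count of missed scheduled assessments, and the SAP does not say which limit to use. Censoring after one missed scan follows if the last ATA sets the year. If the event sets it, the error mainly runs the other way, except on the Week 64 schedule.

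The size is about 1 to 3 of 193 events under the less favourable dating, given the plan's medians, accrual and cut-off, an assumed 5% to 20% of scans missed independently, and the Week 48/60/72 schedule. It is less than half that if the first 12-weekly scan is at Week 56. The hazard ratio shifts by 0.001 to 0.002. The documents do not support a claim that the trial's conclusion is at risk. The reason to act is that an undefined rule should not decide which primary events count.

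**What to change.** Before unblinding:

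1. Replace the day limits in SAP 8.1.2.4 with a direct count. Censor only if two or more consecutive scheduled assessment windows closed without an ATA between the last ATA and the event. This matches protocol 9.2.2.2 and Table 8.
2. State the week of the first 12-weekly scan.
3. Use the same rule in every PFS and duration-of-response analysis that relies on the missed-ATA definition.

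If day limits are kept, derive one for each last-ATA visit whose gap can cross month 12. On the Week 48/60/72 schedule these are 126 days for Week 32, 140 + 21 = 161 for Week 40 and 168 + 21 = 189 for Week 48. The shortest two-miss gaps to a scheduled scan are 175, 203 and 231 days, so these limits separate one missed scan from two. Apply them as more than, not at least, because valid one-miss gaps can equal the limit exactly. Note in the SAP that any day limit can still miscount deaths between visits.

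The cost is a short SAP addendum and a lookup of scheduled visits in the programs. No new data are needed, and the amendment announced in SAP 9.9 could carry the change.
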